Objectives	To determine whether the addition of serial CRP levels (with advice on interpretation) to usual care for managing AECOPD leads to a reduction in antibiotic exposure (defined as the total number of antibiotic days by Day 28) for AECOPD without negatively impacting on COPD health status, compared with usual care alone					
Number of Subjects	N=1,184					
Diagnosis and Main Inclusion Criteria	 Being diagnosed with active AECOPD; AND Known COPD in their medical records; AND Age 40 years or older; AND Able to provide informed consent in Cantonese, Mandarin, or English; AND Able to complete the questionnaires during the study period 					
Participation						
Duration	One year					
Interventions	The intervention group will be recommended to test for CRP at randomization and every day during the stay. Antibiotics are considered for discontinuation when CRP reduces below 5mg/dL, on top of existing clinical judgment. The control group will not be tested for CRP and antibiotics will be discontinued according to clinical judgment.					
Main outcome measures and study instruments	The antibiotic exposure (total number of antibiotic days) and recovery in terms of COPD health status (Clinical COPD Questionnaire total scores) within 28 days from randomization. The secondary outcomes include prevalence of potentially pathogenic bacteria and commensal organisms and their proportion of drug-resistant strain, antibiotics prescribed and total antibiotics consumption (doses), adverse effects potentially attributable to antibiotics prescribed for the exacerbation, general health status, disease-specific, health-related quality of life over time measured using the CRQ-SAS (dyspnoea, fatigue, emotion function, mastery and total scores) and costs (total HA cost) and cost-effectiveness.					
Statistical Methodology	 Baseline subject characteristics: descriptive statistics. COPD-related health status, general health status, and duration of antibiotics: Fisher exact tests. Adverse effects and number of events: Chi squared tests. Between-group difference, CCQ score, and EQ-5D: Students' t-test. Group comparison for categorical variables: Fisher 's Exact test All analyses will be performed using Stata software For missing data handling: multiple imputation methods. Cost evaluations: the healthcare provider using standard methods. Cost-effectiveness analysis during the RCT: ITT principle. Health economic outcomes: QALY. 					

4 of 27 31st Oct 2021 1.1

3. Investigators

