6.6.2 Randomization

Patients will be randomized at ED (Day 1). They are randomised in a 1:1 ratio to receive either usual care alone (control), or usual care with addition of CRP trend monitoring for discontinuation of antibiotics. The randomization sequence will be centralised. Computergenerated and randomly permuted blocks allocations will be used. Exacerbation classification suggested by GOLD Initiative is adopted as a minimisation variable so that balance is achieved with respect to differing levels of COPD exacerbation severity.

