6.6.8 Follow Up

The trial team will aim to contact all participants through telephone call, or audio / video call with instant messaging software and application service such as WhatsApp, WeChat, or Instant Messenger, every week after randomization to follow up CCQ and EQ-5D questionnaires. The patient will be met on video call at 4-weeks post randomization. A copy of Chronic Respiratory Disease Questionnaire, self-administered, standardized (CRQ-SAS) and EQ-5D will be sent to patients for completion and return at 6 months.

Week 1 & Week 3

Follow-up call for *week 1 and 3* (±1 working day): The patient will be interviewed for the symptomatology, CCQ and EQ-5D questionnaires.

Week 4

Clinical follow up at *week 4* (±2 working days) by research clinician for medication consumption, adverse effects, sick leave, diagnosis of pneumonia since the initial encounter, any further CRP tests since the initial encounter, health care consultations, CCQ and EQ-5D. The patient will be required to return to the emergency department to undergo fresh sputum collection, throat swab and nasopharyngeal swab anytime during the day of weekdays before end of week 5. The colour of the sputum specimen will be examined. If the patient defaults the follow up at week 4, the team will contact the patient again and collect as many data items as possible. If the patient is unable to present, follow up call will be performed.

Month 6

At *6-months* post randomisation, the trial team member will examine the patient's medical record for any spirometry results, prescription, and healthcare service utilization. The patient will also be sent a copy of CRQ-SAS and EQ-5D then for self-completion. A text reminder message will be sent through with instant messaging software and application service application. Defaulted patients will be called for interview to collect their responses.

7. Assessment of Efficacy

Mean antibiotic duration (in days) within 28-days for AECOPD after randomization.

8. Assessment of Safety

Adverse Event

Events fulfilling the definition of a serious adverse event (SAE), including death, emergency hospitalization for conditions other than AECOPD, life-threatening medical conditions, (required preventive intervention for) disability or permanent damage, or other serious medical events that occur between randomization and 4-week post randomization will be reported to the trial team as soon as it is detected.

9. Statistics and Data Analysis

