Trained physicians and nurses will help with patient recruitment and data collection in the busy emergency departments.

Baseline subject characteristics will be reported using descriptive statistics such as percentage, medians, and interquartile ranges. COPD-related health status, general health status, and duration of antibiotics use will be compared among groups by Fisher exact tests. Adverse effects and number of events in the intervention group compared to control group will be noted and compared by Chi squared tests.

To estimate the between-group difference on primary outcome of antibiotic duration, two sample T test will be used to the analysis. The other continuous variables including the co-primary outcome (CCQ score) and secondary outcome (EQ-5D) will be analyzed in the same manner.

Fisher 's Exact test will be used to make group comparison for categorical variables such as COPD Severity (GOLD grading), COPD exacerbation severity (Anthonisen criteria) and microbiological pathogen. All available data will be summarized descriptively by tables and figures. All analyses will be performed using Stata software (version 16 or updated version) and considered significant at p<0.05.

For missing data handling, multiple imputation methods will be used to assess the sensitivity of primary outcome results to missing data. Assuming at random, generalised linear models will used for the multiple imputations.

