Primary	To determine whether the addition of a serial CRP levels (with advice on interpretation) to usual care for managing AECOPD leads to a reduction in antibiotic exposure for AECOPD without negatively impacting on COPD health status compared to usual care alone.	Recovery in terms of COPD health status as assessed using the Clinical COPD Questionnaire (CCQ) total scores	2 week
Secondary	To evaluate the effect of serial CRP levels for AECOPD in emergency department on:	Prevalence of potentially pathogenic bacteria cultured from sputum at 4 weeks and the proportion of bacteria that are resistant	4-week
		Prevalence of commensal organisms cultured from sputum at 4 weeks and the proportion of bacteria that are resistant	4-week
		Adverse effects potentially attributable to antibiotics prescribed for the exacerbation	Weekly for 4 weeks
		All-cause antibiotic consumption	During the first 4 weeks post randomisation
			week
		orally administered steroids	4-week
		General health status measured by EuroQol-5D (EQ-5D)	Weekly for 4 weeks
		Primary and secondary care consultations, including hospitalisations	4-week & 6-month
		Costs (total HA cost) and cost-	6 month
		Incidence of pneumonia (measured by patient and medical record)	4-week & 6-momnth
		Disease-specific, health-related quality of life over time measured using the CRQ- SAS (dyspnoea, fatigue, emotion function, mastery and total scores)	6-month

Key: AECOPD acute exacerbation of chronic obstructive pulmonary disease, CCQ Clinical COPD Questionnaire, CRP C-reactive protein point-of-care test, CRQ-SAS Chronic Respiratory Disease Questionnaire, self-administered, standardised

Participant Flow Diagram

CONSORT 2010 Flow Diagram

BRONKOTEST

ERS

Evaluation of sputum colour

Sputum purulence correlates with presence of bacteria and favourable effect of antibiotics

european respiratory society every breath counts

Source: https://www.ersnet.org

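### Chi-squared tests are assigned to numbers of events without saying whether the patient or the event is the unit; if total events are compared, p-values are too small whenever event risk differs between patients.

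*Combined protocol and SAP*

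**What the plan says.** Section 9 (Statistics and Data Analysis) gives the rule: "Adverse effects and number of events in the intervention group compared to control group will be noted and compared by Chi squared tests". The Statistical Methodology entry of Section 2 (Study Summary) shortens it to "Adverse effects and number of events: Chi squared tests". Neither defines an event, says that a patient is counted once, or says that repeat events are pooled.

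Section 9 has a separate rule for categorical variables (Fisher's exact test) and another for continuous variables (two-sample t-test). It names no method for counts or recurrent events. Results are "considered significant at p<0.05"; sidedness is not stated.

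Two outcomes in Appendix 5 bear on this. One is "Adverse effects potentially attributable to antibiotics prescribed for the exacerbation", with time point "Weekly for 4 weeks". The other is "Primary and secondary care consultations, including hospitalisations", at 4 weeks and 6 months. Section 8 (Assessment of Safety) lists serious adverse events, including death and "other serious medical events that occur between randomization and 4-week post randomization".

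**The concern.** A chi-squared test on a table of patients treats each patient as one independent observation, which is correct here. A chi-squared test on event totals treats each event as an independent observation. If some patients are more prone to events than others, their events arrive together, the between-arm difference varies more than the test allows, and chance differences are called significant too often, in either direction.

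At stake is hypothesis (iv) in Section 5.2, that adverse effects of antibiotic treatment will not differ significantly between the groups. A test with excess false positives could wrongly contradict that hypothesis, or wrongly credit the intervention with fewer events. Leaving the unit open also allows the choice between a valid and an anti-conservative test to be made after the data are seen.

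**Working it through.** The plan states no event rate, dispersion or power for these outcomes, so there is no figure of its own to reproduce. The check asks what size the named test has under each reading when there is no treatment effect.

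**Inputs from the documents.** N = 1,184 (Study Summary); "They are randomised in a 1:1 ratio" (Section 6.6.2), hence 1,184 / 2 = 592 per arm; significance level 0.05 (Section 9), taken as two-sided.

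**Assumed inputs.** Mean m of 0.1 to 1.0 events per patient; Poisson counts, or negative binomial counts with gamma shape k from 2 down to 0.25; equal follow-up for all patients. The variance-to-mean ratio of events per patient is φ = 1 for Poisson and φ = 1 + m/k for negative binomial. For example, m = 0.1 and k = 1 give φ = 1.1.

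**Reading 1: total events split by arm.** With event totals A and B, the statistic is (A − B)² / (A + B). Under no effect, A − B has variance 2 × 592 × m × φ, while A + B estimates 2 × 592 × m. The statistic therefore behaves as φ times a chi-squared variable on 1 df, and

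true size = 2 × [1 − Φ(1.96 / √φ)], where Φ is the standard normal distribution function.

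At φ = 2, for instance, 1.96 / √2 = 1.386, which gives 0.166. The simulated column uses 592 per arm and 10,000 replicates; a range covers the several combinations of m and k with the same φ.

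| φ | Formula | Simulated |
|---|---|---|
| 1.0 | 0.050 | 0.047–0.053 |
| 1.1 | 0.062 | 0.056 |
| 1.25 | 0.080 | 0.078 |
| 1.3 | 0.086 | 0.081 |
| 1.5 | 0.110 | 0.109–0.111 |
| 2.0 | 0.166 | 0.162–0.170 |
| 3.0 | 0.258 | 0.257–0.258 |

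The first row matters: repetition alone does no harm here. The inflation comes from differences in risk between patients.

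**Reading 2: events over patients, treated as a proportion in a 2×2 table.** The test uses variance m(1 − m) where the true variance is mφ, so the inflation factor is φ / (1 − m). Even at φ = 1 this is 1 / 0.9 = 1.11 for m = 0.1 (simulated size 0.062) and 1 / 0.5 = 2 for m = 0.5 (simulated 0.170). At m = 0.5 and φ = 3 the simulated size is 0.429. The table cannot be formed once events outnumber patients.

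**Readings with the patient as unit.** Over the same assumed range, the simulated size is:
- patients with at least one event, 2×2 chi-squared: 0.045–0.054;
- patients grouped by 0, 1, 2 or 3+ events, 2×4 chi-squared: 0.035–0.052;
- t-test on the count per patient: 0.044–0.052.

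The test is sound when the patient is the unit. Reading 1 fails once risk differs between patients; reading 2 fails even when it does not.

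**The case against.** A reader might infer that the plan pools repeat events as if independent, so that its p-values are certain to be too small. The documents do not support this. The unit is never stated, and if the sentence means patients with an event, or patients tabulated by number of events, the chi-squared test holds its size. This stands, and it is why the conclusion is conditional.

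The dispersion is also unknown. For uncommon events the ratio may be close to 1, and at 1.1 the size is only about 6%. No passage says that events concentrate in a few frail patients. This stands too; the larger figures illustrate an assumed range and are not forecasts.

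It is an inference that consultations and hospitalisations fall under this test. Section 9 does not name them among the events, the nearest use of the term is for serious adverse events in Section 8, and resource use has its own costing plan in Section 9. For adverse effects, Section 6.6.8 mentions collection only at the week 4 visit, whereas Appendix 5 says weekly, so the data could turn out to be one report per patient. Both limits on scope stand.

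Finally, counts per patient could be placed under the t-test rule for continuous variables, which would be acceptable. But Section 9 does not place them there; it names numbers of events in the chi-squared sentence. That sentence is also separate from the Fisher rule for categorical variables, so it cannot simply be taken as the rule for yes/no outcomes.

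**Conclusion.** The unit of analysis for adverse effects and numbers of events is undefined, and the literal reading, a comparison of event totals, is anti-conservative whenever event risk differs between patients. For totals split by arm, a nominal 5% test has true size of about 5% at a variance-to-mean ratio of 1, rising to 11% at 1.5, 17% at 2 and 26% at 3. This rests on the assumed ratios, two-sided testing and equal follow-up. Deaths and defaulted follow-up, both of which the protocol anticipates, would make time at risk unequal; a plain chi-squared test ignores this, but the documents give no figures from which to size the effect.

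The point concerns secondary and safety outcomes. It does not touch the test of antibiotic duration or of the CCQ score. It merits a change because the repair is cheap and works under every reading.

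**What to change.** Amend Section 9 and the matching line of the Study Summary as follows.

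- For each event type, compare the number of patients with at least one event by a chi-squared test, and report the risk difference with a 95% CI.
- Where numbers of events are compared, use negative binomial regression, or Poisson regression with robust standard errors, with log follow-up time as offset, and report a rate ratio with a 95% CI.
- List which outcomes count as events and over what window, saying explicitly whether consultations and hospitalisations are included. Reconcile Section 6.6.8 with Appendix 5 on whether adverse effects are recorded weekly or only at week 4.

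If event counts are not meant to be tested at all, the first and third items are enough. The cost is a few sentences, standard Stata commands, slightly more analysis work and some wider intervals. No new outcome data are needed; follow-up time can be taken from the dates of planned contacts and of any death. The negative binomial and robust Poisson models were not themselves simulated here; the patient-level t-test on counts, which rests on the same principle, held its size.

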6.6.6 Procedure

The attending emergency physician who sees the patient will report the duration of AECOPD symptoms, medication history, and physical findings (temperature, pulse, oxygen saturation, respiratory rate, abnormal lung sounds and peak expiratory flow rate before and after bronchodilators). The patient was treated according to GOLD initiative, including bronchodilator, and systemic steroid. A sputum sample, a throat swab sample (for bacterial culture) and a nasopharyngeal swab (for respiratory virus – pneumonia panel) are collected. The attending physician will assess and record the sputum colour using the Bronkotest chart (Appendix 8). That patient will be interviewed for CCQ an EQ-5D-5L questionnaire.

Patients randomised to the intervention group will be recommended to have CRP tested and the result will be recorded in the proforma. Medication (including antibiotics) prescription and other management plan will be recorded.

Trial team members will collect healthcare service utilization data, spirometry result, laboratory results and antibiotics prescribed for 12 months before randomization.

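### CCQ and EQ-5D are collected at baseline and weekly, but the planned t-tests use neither the baseline nor the other weekly scores, and no EQ-5D time point is named

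*Combined protocol and SAP*

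**What the plan says.** **Collection.** Section 6.6.6 takes both questionnaires at the initial encounter: "That patient will be interviewed for CCQ an EQ-5D-5L questionnaire". Section 6.6.8 then has the team contact participants "every week after randomization to follow up CCQ and EQ-5D questionnaires", with EQ-5D again at 6 months. Appendix 5 lists EQ-5D for evaluation at each of the first four weeks and CCQ at week 2. Section 10 fixes the CCQ co-primary at day 14 and gives a reason for that choice.

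**Analysis.** For antibiotic duration, Section 9 says a "two sample T test will be used to the analysis", and then "The other continuous variables including the co-primary outcome (CCQ score) and secondary outcome (EQ-5D) will be analyzed in the same manner". All analyses are "considered significant at p<0.05". The section names no repeated-measures model, baseline covariate, main EQ-5D visit or multiplicity rule. It also contains a conflicting instruction: "COPD-related health status, general health status, and duration of antibiotics use will be compared among groups by Fisher exact tests".

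**Missing data.** Section 9 plans multiple imputation under missing at random, to check how sensitive the primary outcome results are. Section 5.2 separates the primary from the co-primary objective, while Appendix 5 labels both as primary. Whether CCQ is covered is therefore unclear, and the variables in the imputation model are not listed.

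**The concern.** The day-14 CCQ carries the non-inferiority claim. A t-test at one visit uses only patients with a score at that visit. A patient with baseline, week 1, week 3 and week 4 scores but no week-2 score adds nothing to the main comparison. The call that matters most also has the least protection: Section 6.6.8 gives windows for weeks 1, 3 and 4 but none for week 2, and describes recontact of defaulters only for week 4 and month 6.

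Two things are at stake for CCQ. One is precision, since baseline and neighbouring scores are collected and left unused. The other is bias: treating physicians know the allocation, so the reasons for missing a call could differ by arm. A lower CCQ is better, so if sicker intervention patients are lost more often, the error favours a false claim of non-inferiority.

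For EQ-5D, hypothesis (iii) expects no significant difference, but nothing says which of four weekly values, the 6-month value or a summary will answer it. The choice could be made after seeing the data, in either direction.

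**Working it through.** **Inputs from the documents.** N = 1,184 (Study Summary), allocated 1:1 (Section 6.6.2), so 592 per arm; significance level 0.05; EQ-5D at weeks 1–4 and month 6. The documents give no missing-data rate, between-visit correlation or CCQ standard deviation, so those below are assumptions. There is no figure in the plan to reproduce on this point.

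**1. Precision from the other weekly scores.** Assume 15% miss day 14 and weeks 1, 3 and 4 are complete.
- Missing: 0.15 × 1,184 ≈ 178. Remaining in the t-test: about 1,006.
- With equal correlation ρ, the share of week-2 variance explained by the other three weeks is R² = 3ρ²/(1 + 2ρ). For ρ = 0.6, 1.08/2.2 = 0.49. For ρ = 0.7, 1.47/2.4 = 0.61.
- The variance of the week-2 estimate is proportional to (1 − R²)/1,006 + R²/1,184, and effective N is its inverse.

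| ρ | Effective N | Gain | SE ratio to t-test |
|---|---|---|---|
| 0.6 | 1,086 | 80 | √(1,006/1,086) = 0.96 |
| 0.7 | 1,108 | 102 | √(1,006/1,108) = 0.95 |

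If only half of the 178 have the other weeks, replace 1,184 by 1,006 + 89 = 1,095. The gain falls to about 42–53 patients, and the standard error by only 2–2.5%.

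**2. Precision from baseline.** With complete data, adjusting for a baseline correlated r with day 14 multiplies the variance by 1 − r². This is 0.64 at r = 0.6, but 0.91 at r = 0.3. The lower value deserves attention because baseline is taken during the exacerbation. If baseline correlates with each visit as the visits do with each other (0.6), baseline and weekly scores together give a variance ratio to the t-test of 0.625 with 10% missing and 0.609 with 20%. Most of that gain comes from baseline. Once it is in the model, the other weeks explain only 24% of the remaining week-2 variance.

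**3. Bias.** Large simulation, 400,000 per arm: four visits, mean 2.5, SD 1.2, correlation 0.6, no true difference. The probability of missing week 2 is logistic in week-1 CCQ, with intercept −1.9 and slope b.

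| b control / intervention | Missing (control / intervention) | t-test difference | Using other visits |
|---|---|---|---|
| 0.5 / 0.5 | 14.5% / 14.4% | 0.001 | 0.001 |
| 0.3 / 0.8 | 13.5% / 16.5% | −0.067 | −0.001 |
| 0 / 0.8 | 13.0% / 16.4% | −0.096 | 0.004 |

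Negative values favour the intervention. Swapping the slopes between arms would reverse the sign.

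**4. EQ-5D.** If k visits were each tested at 0.05, independent tests give 1 − 0.95^k: 18.5% for k = 4 and 22.6% for k = 5. With equally correlated normal statistics (1,000,000 draws):

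| Correlation | 4 tests | 5 tests |
|---|---|---|
| 0.5 | 15.6% | 18.3% |
| 0.8 | 11.4% | 12.7% |

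One contrast named in advance returns this to 5%.

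**The case against.** The strongest reply is that day 14 is a legitimate, reasoned single endpoint. A t-test at that visit is a valid comparison, and it creates no multiplicity for CCQ. That stands, and the proposal keeps the endpoint. What remains is a choice of estimator, and the gain from the other weeks alone is modest.

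Three stronger readings are tempting, and the documents do not support them.
- A reader might infer that patients who miss day 14 are lost to the trial's inference altogether. Imputation is planned, and Appendix 5's labelling arguably brings CCQ within it. It is still only a sensitivity analysis with unstated predictors, so the main comparison remains one of completers.
- A reader might infer that EQ-5D will be tested four or five times. Section 9 never says so. Appendix 5 gives an evaluation schedule, and Section 9 also uses the repeated utilities for QALYs. The gap is that no visit or summary is designated for hypothesis (iii). Extra false positives would count against that hypothesis, and a single non-significant test would not establish equivalence either.
- A reader might multiply the 178 missing patients by R² and claim 87–109 recovered. That is not the information gained; the variance formula gives 80–102 at best.

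It is also fair that bias is not shown. It appears only when the missingness mechanism differs by arm, and nothing in the documents establishes that it will.

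**Conclusion.** The concern holds, mainly for CCQ. The main co-primary analysis leaves out patients without a day-14 score and ignores both baseline and neighbouring weekly scores, although all are collected. Under 15% missingness, correlation 0.6–0.7 and complete other weeks, using the weekly scores adds the equivalent of about 80–102 patients, and less if those weeks are also missing. Baseline adjustment may add considerably more, depending on how well an exacerbation-time score predicts day 14. A bias of roughly 0.07–0.10 CCQ points is possible under the assumed arm-differential mechanisms. With no true difference and the same mechanism in both arms, none is expected.

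The EQ-5D part is lesser: an unstated choice on a secondary outcome, with an 11–18% false-positive risk only if every visit were tested. The change is worth making because it costs almost nothing and protects a co-primary estimate. The evidence does not show that the planned analysis is invalid.

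**What to change.** In Section 9 and the Study Summary:

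- **CCQ.** Keep day 14 as the co-primary time point. Estimate the arm difference and its CI as the week-2 contrast from one mixed model for repeated measures over weeks 1–4, with arm, week, arm-by-week, baseline CCQ and baseline-by-week, and unstructured covariance.
- **EQ-5D.** Use the same type of model with baseline EQ-5D. Name one contrast in advance as the single test, for example the average difference over weeks 1–4. Report the other time points, including month 6, as estimates with CIs.
- **Conflicting text.** State that these models replace both the t-test and the Fisher exact test for these outcomes.
- **Imputation.** State whether it covers CCQ, and include baseline and the other weekly scores in any imputation model.

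The cost is a wording change and slightly more analysis work with standard Stata commands, with no new data or visits. The downside is that the main CCQ result then relies on missing at random given the observed scores, an assumption the plan already makes for its imputation.

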5.1 Clinical Question

In adult AECOPD patients in Emergency Departments, does CRP-guided antibiotic treatment, compared with usual care, lead to shorter antibiotic duration without negatively impact on clinical COPD-health status?

5.2 Aims and Hypotheses to be Tested:

This study seeks to establish whether serial CRP level guided clinical judgment can safely and cost-effectively be used to better target antibiotic treatment (include both treatment and discontinuation) for AECOPD in emergency departments to those that are most likely to benefit, so that overall antibiotic exposure duration is decreased without compromising COPD-related health status.

The **primary** objective is to determine whether the addition of a serial CRP levels to usual care for AECOPD leads to shorter antibiotic duration,

The **co-primary objective** is to determine whether the addition of a serial CRP levels to usual care for AECOPD is non-inferior to usual care alone, on COPD health status as measured by CCQ

The **secondary objectives** are the effectiveness of the addition of serial CRP levels to usual care in AECOPD patients on:

- General health status as measured by EQ-5D-5L
- Adverse effects of antibiotics
- Cost-effectiveness of individualised CRP-guided antibiotic treatments.

Primary and secondary objectives and outcome measures are listed in Appendix 5.

We hypothesise that:

- (i) antibiotic duration (defined as 'the number of days of antibiotic treatment') in 28 days among AECOPD patients will be significantly lower for CRP-guided antibiotic treatment (including prescription and discontinuation) than usual care
- (ii) COPD health status as measured by the Clinical COPD Questionnaire (CCQ) has no statistically significant difference between two groups;

- (iii) general health status of AECOPD patients as measured by EQ-5D-5L will not be significantly different between the two groups
- (iv) adverse effects of antibiotic treatment in AECOPD patients will not be significantly different between the two groups
- (v) CRP-guided antibiotic treatment will be more cost-effective than usual care

6. Study design

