Secondary outcome measures include adverse effects potentially attributable to antibiotics prescribed for the exacerbation, general health status measured by EuroQoI-5D (EQ-5D),

Costs (total HA cost) and cost-effectiveness, Disease-specific, health-related quality of life over time measured using the CRQ-SAS (dyspnoea, fatigue, emotion function, mastery and total scores).

11. Direct Access to Source Data/ Documents

The investigators and the research assistants in the research team will be responsible for data collection of the project. The investigators will permit trial-related monitoring, audits, IRB review, and regulatory inspection(s), providing direct access to source data and documents.

12. Ethics

The trial will be conducted in accordance with the principles originating in the Declaration of Helsinki, and those in Good Clinical Practice. After patients (or relatives/legal representatives) are assessed as suitable for the Trial, all subjects for this study will be provided a consent form describing this study and providing sufficient information for subjects to make an informed decision about their participation in this study. This consent form is submitted with the protocol for review and approval by the Institutional Review Board (IRB) for the study. The formal consent of a subject, using the IRB-approved consent form, must be obtained before that subject is submitted to any study procedure. This consent form must be signed by the subject or legally acceptable surrogate, and the investigator-designated research professional obtaining the consent. The trial will be conducted in accordance with the information and consent forms.

13. Data Handling and Record Keeping

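### Secondary outcomes are judged at an unadjusted p<0.05 with no testing order or exploratory label, so chance findings among them could be reported as significant effects

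*Combined protocol and SAP*

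**What the plan says.** Section 9 (Statistics and Data Analysis) has a single decision rule: "All analyses will be performed using Stata software (version 16 or updated version) and considered significant at p<0.05". It sends EQ-5D to the same two-sample t test as the primary outcome, adverse effects to chi-squared tests, and makes a "group comparison for categorical variables such as COPD Severity (GOLD grading), COPD exacerbation severity (Anthonisen criteria) and microbiological pathogen" by Fisher's exact test. The same section says baseline characteristics are reported descriptively.

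The secondary outcomes appear in four places.

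- Section 5.2 introduces them with "The secondary objectives are the effectiveness of the addition of serial CRP levels to usual care in AECOPD patients on" and lists three: EQ-5D-5L, adverse effects of antibiotics, and cost-effectiveness. Hypotheses (iii) to (v) on these stand beside the two primary hypotheses. The section then refers to Appendix 5 for the objectives and outcome measures.
- Section 10 begins "Secondary outcome measures include adverse effects potentially attributable to antibiotics prescribed for the exacerbation" and adds EQ-5D, costs and cost-effectiveness, and CRQ-SAS.
- The Study Summary (section 2) states "The secondary outcomes include prevalence of potentially pathogenic bacteria and commensal organisms and their proportion of drug-resistant strain", and also names antibiotic consumption.
- Appendix 5 is the longest list. It adds oral steroids, consultations including hospitalisations, and "Incidence of pneumonia (measured by patient and medical record", the last two each at 4 weeks and 6 months. It also has "Disease-specific, health-related quality of life over time measured using the CRQ- SAS (dyspnoea, fatigue, emotion function, mastery and total scores", which is five scores.

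**The concern.** A rule that covers all analyses covers the secondary outcomes too. Followed as written, it allows a p<0.05 on resistance, pneumonia or one CRQ-SAS domain to be reported as a significant effect of CRP guidance, with nothing to warn the reader that it is one of many comparisons. This matters most if the main result is mixed, which is possible because the trial needs superiority on antibiotic duration and non-inferiority on CCQ. An isolated secondary result could then carry the message.

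A second risk runs the other way. Hypotheses (iii) and (iv) predict no significant difference in general health status and adverse effects. Under a bare p<0.05 rule, a non-significant result could be taken to confirm them, although it does not show that the arms are equivalent.

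**Working it through.** **The plan's own figure.** The documents give no family-wise error rate for the secondary outcomes, so there is none to reproduce. The only error figure is "considered significant at p<0.05", a threshold for each test. Sidedness is not stated; two-sided is assumed.

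**Counting the tests.**

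- Section 5.2: 3 objectives, so k = 3.
- Appendix 5, readable rows: microbiology 4 (prevalence and resistance, for pathogens and for commensals), adverse effects 1, oral steroids 1, EQ-5D 1, consultations and hospitalisations 2 (two time points), pneumonia 2 (two time points), CRQ-SAS 5. The sum is 4 + 1 + 1 + 1 + 2 + 2 + 5 = 16.
- Left out of the 16: cost, because section 9 assesses it by an incremental ratio with sensitivity analyses and not clearly by a p-value; antibiotic consumption, because it overlaps the primary outcome and is not a true null if the intervention works; and one row that cannot be read. EQ-5D and adverse effects are counted once although Appendix 5 lists them weekly for 4 weeks.

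**Formulas (all null hypotheses true).**

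- Independent tests, either direction: 1 − 0.95^k.
- Independent tests, favourable direction only: 1 − 0.975^k.
- Correlated tests: equicorrelated normal statistics with correlation ρ, by numerical integration of 1 − ∫ φ(u) [Φ((c − √ρ·u)/√(1−ρ)) − Φ((−c − √ρ·u)/√(1−ρ))]^k du, with c = 1.96. For favourable errors only, the second Φ term is dropped.

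The documents give no correlations; 0, 0.5 and 0.8 are assumptions.

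**Results: chance of at least one p<0.05.**

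| Family | ρ = 0 | ρ = 0.5 | ρ = 0.8 |
|---|---|---|---|
| k = 3, either direction | 14.3% | 12.5% | 9.8% |
| k = 16, either direction | 56.0% | 37.4% | 20.7% |
| k = 16, favourable only | 33.3% | 18.8% | 10.4% |

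By hand at ρ = 0: 1 − 0.95^3 = 1 − 0.857 = 0.143; 1 − 0.95^16 = 1 − 0.440 = 0.560; 1 − 0.975^16 = 1 − 0.667 = 0.333. The expected number of false positives among 16 true nulls is 16 × 0.05 = 0.8, whatever the correlation.

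**Sensitivity to the count.** Putting cost and consumption back gives k = 18: 60.3%, 39.8% and 21.6%. Also testing EQ-5D and adverse effects weekly adds 3 + 3, so k = 24: 70.8%, 45.8% and 23.8%. The chance passes 50% only from k = 14 under independence, k = 18 at ρ = 0.3 and k = 30 at ρ = 0.5.

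**The case against.** The strongest reply is that the plan already separates primary and co-primary from secondary outcomes, defines the trial by the two co-primaries, and states 5% per test without promising a 5% family-wise rate. Multiplicity among secondary outcomes leaves the co-primary error rates unchanged. All of this stands, and it limits the point to how secondary results may be claimed. It does not remove the point, because the section 9 rule applies to those results and nothing readable qualifies it.

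A reader might go further and infer that a false significant secondary result is likely. The documents do not support that. Even 16 tests pass 50% only near independence, and independence is implausible: the CRQ-SAS total is built from its domains, and a 4-week pneumonia also counts at 6 months. The figures also need every null to be true.

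A reader might also infer from the four differing lists that the secondary family is undefined, so that a chance finding could later be presented as pre-specified. That is largely answered. Section 5.2 names Appendix 5 as the list, and sections 2 and 10 are worded as partial lists. What remains is tidying.

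Lastly, a reader might take the Fisher tests of GOLD grade and Anthonisen severity as tests of baseline balance. Section 9 does not say when these are measured. The timing is an inference, so this is a conditional, minor remark.

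**Conclusion.** The point holds as a reporting weakness that should be corrected. Secondary comparisons are judged at an unadjusted p<0.05, with no testing order or exploratory label in the readable text. The size depends on the family: about 10% to 14% for the section 5.2 objectives, and about 21% to 56% for the 16 Appendix 5 tests, of which errors in favour of the intervention account for about 10% to 33%. These figures assume that all secondary nulls are true, two-sided tests, and a common correlation between 0.8 and 0. They describe exposure to chance findings and do not predict that one will occur. For EQ-5D and adverse effects, where no difference is hypothesised, the larger risk is that p>0.05 is read as equivalence.

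**What to change.** In section 9, replace the blanket rule with the following.

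1. Confirmatory claims are limited to the two co-primary outcomes. Antibiotic duration is tested for superiority at p<0.05. CCQ is judged by its confidence interval against the non-inferiority margin, not by a p<0.05 test of difference.
2. All secondary outcomes are exploratory and reported as effect estimates with 95% confidence intervals, without significance claims. No Bonferroni-type penalty is applied to adverse effects, pneumonia or hospitalisation, so that a harm signal is not hidden.
3. Hypotheses (iii) and (iv) in section 5.2 are reworded in terms of estimation, so that a non-significant difference is not taken as evidence of equivalence.

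Minor: align sections 2, 5.2 and 10 with Appendix 5. Where GOLD grade and Anthonisen severity are entry characteristics, show them descriptively without between-arm tests.

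The cost is wording only, with no new data or patients. The one loss is that a secondary result can no longer be called statistically significant on p<0.05 alone.
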